5.2.2 Post-vaccination Reminders

Reminder calls (or emails) are not intended to be an interview for collection of safety data. If the subject wishes to describe safety information, this information should only be collected by a healthcare professional at the site, and the safety data described must be written down in the subject's medical chart/source document.

Subject Diary Reminder Calls / Emails

Subject Diary reminder calls will be performed or email will be sent on day 3 and day 7 post vaccination. The purpose of this call or email is to remind the subject about completion of the Subject Diary. The call/email follow the Subject Diary Reminder Telephone Call/Email Scripts provided to the site. The subject should be reminded to contact the site via the telephone number provided in the informed consent to discuss medical questions. The safety data described by the subject on a telephone call must be written down in source documents and the subject should be reminded to write the information down in the diary card, as applicable.

If the email is printed by study staff to document that the reminder was sent, all personal information such as name and email address of the subject, will be removed before printing.

5.3 Post-vaccination Visit(s)

5.3.1 Follow-up Clinic Visit(s)

Safety follow-up clinic visits will be performed on day 8, day 15, day 29 and day 85.

During visit 2, the Subject Diary will be reviewed. No changes to the information recorded within the Subject Diary are permissible. For details on the Subject Diary see [sections 3.4.2, Tools Used for Data Collection](#) and [5.2.1, Post-vaccination Procedures](#). The subject will be interviewed to determine if any unsolicited adverse events occurred and if any concomitant medications or vaccines were taken or received in the time since the last visit. This interview will follow a checklist which will facilitate the collection of relevant safety information. The healthcare professional reviewing these data will discuss the symptoms (if any) reported by the subject and will determine if any additional diagnoses and/or adverse events are present. Adverse events reported by the subject at this follow-up clinic visit must be recorded in the subject's source document and on an Adverse Events eCRF, as specified in [section 7.1, Safety Assessment](#), and not written on the checklist used for the interview.

Perform a brief symptom-directed physical examination if necessary according to symptoms the subject has reported. This is a physical examination that will include an examination of organ systems that are relevant to the investigator based on review of the subject's reported adverse events, concomitant medication use. The physical assessment must be performed by the investigator or designee of the investigator, who is qualified to perform a physical assessment in accordance with their institutional policy. Corresponding information is documented in the subject's source document.

The site should schedule the next study activity, i.e. the next clinic visit and reminder phone call/email with the subject. The subject will be reminded to contact the site if there are any questions and to contact the site immediately (or as soon as the subject is medically stable) if the subject has a medical condition that leads to a hospitalization or an emergency room visit.

5.3.2 Safety Follow-up Calls

No safety follow up call will be made in this study. [5.4](#)

Unscheduled Visits

An unscheduled visit describes a non-routine study visit triggered by a specific event. These could include anticipated or unanticipated adverse events or interventions. Data obtained from such unscheduled visit should be record in a respective source document and eCRF.

If a case of neutropenia is observed after vaccination and still prevalent on a subsequent visit, the results will be recorded in the Unscheduled Lab eCRF.

All individuals with a neutropenia, occurring at any time during the study, will have additional blood draws for complete blood count to be repeated on a weekly basis until the neutropenia resolves. If neutropenia occurs at the subject's last study visit, the complete blood count will be repeated on a regular basis until resolution. For classification of neutropenia during the trial, refer to [section 7.1.4.1 Adverse Events of Special Interest](#).

5.5 Study Termination Visit

The study termination visit will occur on day 85 (visit 5). The date of termination is the date of the last contact (clinic visit or telephone call) in which the subject's health status was assessed or, in cases where the subject does not agree to any further safety follow-up; it is the date consent is withdrawn. This date should be recorded on the termination eCRF page. For visit procedures to be performed for a subject whose planned study participation ends prematurely, please see [section 5.5.1, Early Termination Visit](#).

At the clinic visit or during the telephone call, the following procedures will be performed:

Review of systems, interview of subject to collect: medically attended adverse events, AEs leading to withdrawal, SAEs, AESIs, and new onset of chronic disease, interview of subject to collect concomitant medications in relation to these events, vaccinations, symptom-directed physical assessment and a check of general appearance, blood sampling for safety laboratory assessment (hematology testing) and immunogenicity, and a urine pregnancy test for women of childbearing potential.

The site will review with the subject the plan of when information relating to the subject's participation in the study may be available (i.e., study results, treatment assignments).

The site will complete the termination eCRF page and this will mark the completion of the subject's participation in the study.

5.5.1 Early Termination Visit

When a subject is withdrawn from treatment or withdraws from the study, the investigator will notify the Sponsor and, when possible, will perform the procedures listed below. The reason(s) for the early termination will be included in the subject's source documentation. If the Early Termination Visit is a telephone call, collect as much information as possible. Early Termination Visits include subjects who were enrolled but not treated.

At the clinic visit, the following procedures will be performed;

- Review of subject's medical records, source document and Diary Card,

- Review of systems, interview of subject to collect unsolicited adverse events, medically attended adverse events, AEs leading to withdrawal, SAEs, AESIs, and new onset of chronic disease,
- Interview of subject to collect concomitant medications/vaccinations,
- Symptom-directed physical assessment including measurement of vital signs and a check of general appearance,
- Blood sampling for safety laboratory assessment (no blood for immunogenicity assessment should be obtained unless this is agreed in advance with the Sponsor),
- Urine sample for pregnancy testing.

All individuals with neutropenia either ongoing or with onset at last study visit will have additional blood draws for complete blood count to be repeated on a regular basis until the neutropenia resolves (for classification of neutropenia during the trial, refer to [section 7.1.4.1 Adverse Events of Special Interest](#)). Laboratory results obtained after study termination will be maintained in subject medical records and not entered in the eCRF.

The site will review with the subject the plan of when information relating to the subject's participation in the study may be available (e.g., study results, treatment assignments). It will also be discussed how information relating to the subject's participation in the study will be shared with the subject's healthcare provider, if the subject chooses to share this information.

The site will complete the termination CRF page and this will mark the completion of the subject's participation in the study.

6. TREATMENT OF SUBJECTS

All vaccines associated with this study are to be stored separately from other vaccines and medications in a secure location under appropriate storage conditions with temperature monitoring. **All vaccines associated with this study must be checked for expiration date prior to use. Expired vaccines must not be administered to subjects.**

6.1 Study Vaccine(s)

The term 'study vaccine' refers to those vaccines provided by the Sponsor, which will be evaluated as part of the study objectives. The study vaccine specific to this study is GVGH *S. sonnei* 1790GAHB vaccine. The GVGH GAHB-Placebo will be used as diluent for bedside mixing as described below.

The investigational agent is the GVGH *S. sonnei* vaccine. The vaccine consists of *S. sonnei* 1790-GMMA (200 µg/mL, measured by protein content) adsorbed to Alhydrogel®, (0.7 mg Al3+/mL) in Tris-buffered saline. The vaccine does not contain any preservative and is available as a liquid formulation in single dose vials with 0.7 mL of injectable

solution containing approximately 140 µg of GMMA (as protein content), adsorbed onto 0.49 mg Al3+. It should be stored at +2/+8 °C.

A diluent, named GAHB-Placebo, visually matching the *S. sonnei* 1790GAHB vaccine, is also supplied for use in this clinical study as a diluent for bedside mixing. It contains the same formulation ingredients as the active *S. sonnei* 1790GAHB vaccine, except for the Drug Substance antigen 1790-GMMA, and is provided in the same primary packaging as the *S. sonnei* 1790GAHB vaccine.

Aluminum hydroxide is well characterized and used as adjuvant in several licensed vaccines. In 1790GAHB, aluminum hydroxide is used as an adsorbent to reduce the reactogenicity of LPS and does not enhance the immunogenicity of the GMMA vaccine. For further information of study vaccines refer to the Investigator Brochure. **6.2 Non-Study Vaccines**

There will be no non-study vaccines to be used.

6.3 Vaccine Preparation and Administration

The investigator or designee will be responsible for oversight of the administration of vaccine to subjects enrolled in the study according to the procedures stipulated in this study protocol. All vaccines will be administered only by personnel who are qualified to perform that function under applicable local laws and regulations for the specific study site.

Detailed vaccine preparation and administration instructions will be provided to investigators in the bedside mixing checklist and instructions prior to study start.

A *S. sonnei* 1790GAHB vaccine volume of 0.5 mL will be administered intramuscularly after bedside mixing to make a 25 µg protein/0.5 mL dose. Bedside mixing, possibly necessary additional labeling of clinical study materials at the study site and vaccine administration will be performed according to Sponsor instructions and by trained site staff. The site staff responsible for these activities will be personnel who are respectively qualified according to applicable local laws and regulations. Sponsor will provide specific procedures and training for these activities.

PRECAUTIONS TO BE TAKEN IN ADMINISTERING STUDY VACCINE:

Prior to vaccination, subjects must be determined to be eligible for study vaccination and it must be clinically appropriate in the judgment of the investigator to vaccinate. Eligibility for vaccination prior to first study vaccine administration is determined by evaluating the entry criteria outlined in protocol [sections 4.1, Inclusion Criteria](#) and [4.2, Exclusion Criteria](#).

Study vaccines should not be administered to individuals with known hypersensitivity to any component of the vaccines.

Standard immunization practices are to be observed and care should be taken to administer the injection intramuscularly. Before administering vaccine, the vaccination site is to be disinfected with a skin disinfectant (e.g., 70% alcohol). Allow the skin to dry. **DO NOT inject intravascularly.**

As with all injectable vaccines, trained medical personnel and appropriate medical treatment should be readily available in case of anaphylactic reactions following vaccine administration. For example, epinephrine 1:1000, diphenhydramine, and/or other medications for treating anaphylaxis should be available.

6.3.1 Replacement of unusable vaccines

In addition to the vaccine doses provided for the planned number of subjects (including extra doses to allow flexibility in enrolment at the different sites), at least 5% additional vaccine doses will be supplied to replace those that are unusable.

6.4 Vaccine Administration Error or Overdose of Vaccine

Vaccine administration error is defined as receiving a dose of study vaccine that was not prepared according to bedside mixing instructions or administered by a different route from the intended route of administration. An overdose of study vaccine (whether accidental or intentional) is defined when a dose higher than dose foreseen in this clinical study, i.e. 25 µg is administered in one dose of *Shigella sonnei* 1790GAHB study vaccine subjects.

Any vaccine administration error or overdose of study vaccine detailed in this protocol must be reported as an adverse event, and if the vaccine administration error or overdose is associated with a serious adverse event, it must be reported as such within 24 hours to the Sponsor.

6.5 Prior and Concomitant Medications and Vaccines

All relevant medications taken or received by the subject within 4 weeks prior to the start of the study are to be recorded on the Prior and Concomitant Medications eCRF.

In addition, the following are considered prior medications for this protocol:

all medication/vaccines described in the inclusion and exclusion criteria of this protocol including the use of antipyretics and/or analgesic medications within 24 hours prior to vaccination and ending 12 hours after vaccination must be identified and the reason for their use (prophylaxis versus treatment) must be described in the source document and Concomitant Medications CRF [Section 4.3, Criteria for Delay of Vaccination](#). Use of antipyretic, 24 hours before vaccination is a reason to delay vaccination.

Medications taken for prophylaxis are those intended to prevent the onset of symptoms. Medications taken for treatment are intended to reduce or eliminate the presence of symptoms that are present.

Concomitant medications include all medications (including vaccines) taken by/administered to the subject at and after enrolment and must be documented on the Concomitant Medications CRF.

When recording concomitant medications/vaccines, they should be checked against the study entry and continuation criteria in [section 4, Selection of Study Population](#) to ensure that the subject should be enrolled/continue in the study.

6.6 Vaccine Supply, Labeling, Storage and Tracking

Detailed vaccine supply, labeling, storage and tracking instructions will be provided to investigators prior to study start.

The Sponsor will ensure the following:

- Supply the study vaccine.
- Appropriate labeling of all study that complies with the country legal requirements.

The investigator must ensure the following:

- Acknowledge receipt of the study vaccines by a designated staff member at the site, including confirmation that the vaccines were received in good condition.
- Proper storage of the study vaccines, including:
 - Storage in a secure, locked, temperature-controlled location.
 - The study vaccine must be stored at the respective label storage temperature conditions in a safe and locked place. Access to the storage space should be limited to authorized study personnel. The storage conditions will be assessed during pre-study activities under the responsibility of the sponsor study contact.
 - Proper storage according to the instructions specified on the labels.
 - Appropriate record keeping and inventory of the study vaccines, including regular documentation of adequate storage temperature.
 - The storage temperature should be continuously monitored with calibrated (if not validated) temperature monitoring device(s) and recorded.
 - Temperature excursions must be reported in degree Celsius.
 - Any temperature excursion outside the range of +2.0 to +8.0 °C impacting investigational medicinal products (IMPs) must be reported to the Sponsor. The impacted IMPs must not be used and must be stored in quarantine at label temperature conditions until usage approval has been obtained from the Sponsor.
- Appropriate use of the study vaccines, including:
 - Use only in accordance with the approved protocol.

- Proper handling, including confirmation that the vaccine has not expired prior to administration.
- Appropriate documentation of administration of vaccines to study subjects including:
 - Date, dosage, batch/lot numbers, expiration dates, unique identifying numbers assigned to subjects and study vaccines, and time of vaccine administration. This information will be maintained in an accountability log that will be reviewed by the site monitor.
 - Reconciliation of all vaccines received from the Sponsor. Reconciliation is defined as maintaining records of which and how many vaccines were received, which vaccines were administered to subjects, which vaccines were destroyed at the site, and which vaccines were returned to the Sponsor, as applicable.
- Proper adherence to the local institutional policy with respect to destruction of study vaccines.
- Complete record keeping of vaccine use, wastage, return or destruction, including documentation of:
 - Copy of the site's procedure for destruction of hazardous material. - Copy of Destruction Certificate.

Vaccines that have been stored differently from the manufacturer's indications **must not** be used unless the Sponsor provides authorization for use. In the event that the use cannot be authorized, the Sponsor will make every effort to replace the vaccine supply. All vaccines used in conjunction with this protocol must be stored separately from normal hospital/practice stocks to prevent unintentional use of study vaccines outside of the clinical study setting.

Monitoring of vaccine accountability will be performed by the study monitor during site visits and at the completion of the study.

At the conclusion of the study, and as appropriate during the course of the study, the investigator must ensure that all unused study vaccines, packaging and supplementary labels are destroyed locally (upon approval from the Sponsor) or returned to the Sponsor.

7. ASSESSMENTS

7.1 Safety Assessment

The measures of safety used in this study are based on previous study data. They include a close vigilance for, and stringent reporting of selected local and systemic adverse events routinely monitored in vaccine studies as indicators of reactogenicity.

An adverse event (AE) is defined as any untoward medical occurrence in a subject or clinical investigation subject administered a pharmaceutical product at any dose that does not necessarily have to have a causal relationship with this treatment. Therefore, an AE can be any unfavorable and unintended sign (including an abnormal laboratory finding, for example), symptom, or disease temporally associated with the use of an investigational product, whether or not considered related to the investigational product. This definition includes intercurrent illnesses or injuries and exacerbation of pre-existing conditions.

For the purpose of this trial, AEs will be from the time the subject signs informed consent until Visit 4. AEs occurring after the informed consent form is signed but prior to receiving study vaccine will be documented as an adverse event and recorded within source document. However, any AEs occurring prior to receipt of any study vaccine will be analyzed separately from “treatment emergent” AEs (AEs occurring after administration of the first study vaccine). All adverse events that are serious, clinically significant as judged by the investigators, medically attended and AESI will be collected until study termination at visit 5.

Adverse events are collected as either solicited or unsolicited adverse events. Solicited events are derived from organized data collection systems, such as Subject Diaries or interview.

7.1.1 **Solicited Adverse Events**

The term “reactogenicity” refers to solicited signs and symptoms (“solicited adverse events”) occurring in the hours and days following a vaccination, to be collected by the subject for 7 consecutive days, using a pre-defined Subject Diary.

The following solicited adverse events are included in the Subject Diary. Each adverse event is to be assessed using the scoring system reported in parentheses below:

Solicited Local Adverse Events

These include erythema, induration and pain at injection site. They will be assessed using the scoring system reported in a table below. **Table 6 Grading of solicited local adverse events**

Solicited local adverse events	Grade 0 Absent	Present - Grading of Severity		
		Grade 1 Mild	Grade 2 Moderate	Grade 3 Severe
Injection site Erythema (Captured as measurements in millimeters)	1-24 mm	25-50 mm	51-100 mm	> 100 mm

Injection site Induration (Captured as measurements in millimeters)	1-24 mm	25-50 mm	51-100 mm	> 100 mm
Injection site Pain	No pain	Present but does not interfere with activity	Interferes with activity	Prevents daily activity

Solicited Systemic Adverse Events

These include headache, arthralgia, chills, fatigue, malaise, myalgia, and fever (body temperature measured orally). They will be assessed using the scoring system reported in a table below.

Table 7 Grading of solicited systemic adverse events

Solicited systemic adverse events	Grade 0 Absent	Present - Grading of Severity*		
		Grade 1 Mild	Grade 2 Moderate	Grade 3 Severe
Headache	No headache	Present but does not interfere with activity	Interferes with activity	Prevents daily activity
Arthralgia	No arthralgia	Present but does not interfere with activity	Interferes with activity	Prevents daily activity
Chills	No chills	Present but does not interfere with activity	Interferes with activity	Prevents daily activity
Fatigue	No fatigue	No interference with activity	Some interference	Significant; prevents daily
			with activity	activity
Malaise	No malaise	No interference with activity	Some interference with activity	Significant; prevents daily activity
Myalgia	No myalgia	Present but does not interfere with activity	Interferes with activity	Prevents daily activity
Fever as a Body temperature (Captured as measurements in degrees Celsius)	≤ 37.9 °C	≥ 38.0 – 38.9°C	≥ 39.0 – 39.9°C	≥ 40.0°C
	Oral Temperature: <35.5 °C to ≥38.0 °C			

Other Solicited Adverse Events

These include use of analgesics/antipyretics. It will be assessed using the scoring system reported in a table below.

Other Solicited adverse events	Grade 0 Absent	Present - Grading of Severity			
		Grade 1 Mild	Grade 2 Moderate	Grade 3 Severe	
Use of analgesics/ antipyretics		Categorized as “yes” or “no”			

The study staff must review the data entered into the Subject Diary as described in [section 3.4.2, Tools Used for Data Collection](#) and [section 5.3.1, Follow-up Clinic Visit\(s\)](#).

Note: Any solicited adverse event that meets any of the following criteria must be entered into subjects’ source document (see [section 9.1, Source Documentation](#)) and also as an adverse event on the Adverse Event CRF:

- Solicited local or systemic adverse event that continues beyond day 7 after vaccination.
- Solicited local or systemic adverse event that leads to a visit to a healthcare provider (medically attended adverse event, see [section 7.1.3, Evaluation of Adverse Events](#)).
- Solicited local or systemic adverse event leading to the subject withdrawing from the study or the subject being withdrawn from the study by the investigator (adverse event leading to withdrawal, see [section 7.1.3, Evaluation of Adverse Events](#)).
- Solicited local or systemic adverse event that otherwise meets the definition of a serious adverse event (see [section 7.1.4, Serious Adverse Events](#)).

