7.1.7 Safety Laboratory Measurements

For list of safety laboratory measurement, refer to synopsis [Table 2, Hematological Safety](#) [Table 3](#).

Safety laboratory measurement will be performed as described in [Section 3.5, Collection of Clinical Specimens](#).

Significant alterations in hematology will be clinically assessed by the investigator's medical judgment based on interpretation of deviations from institution's normal values.

Any abnormality in laboratory measurements classified as clinically significant must be reported in the Adverse Event CRF form.

If a subject is to have blood drawn testing for safety laboratory for repeat safety assessment (i.e., in case of markedly abnormal safety laboratory parameter), investigator's medical judgment will be applied concerning values that would trigger reanalysis and frequency of repeats. If neutropenia is observed at a visit, a complete blood count will be repeated on a weekly basis until resolution.

Safety laboratory assessments will be performed at the site laboratory, and results of these tests will be recorded in the source documents and in the CRF.

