Clinically significant modifications in hematology will be assessed by medical judgment and recommendations from CBER FDA guidance for Industry; Toxicity Grading

Vaccination Procedure:

All eligible subjects will receive one intramuscular vaccination with GVGH *S. sonnei* 1790GAHB vaccine. Subjects will be observed at the clinic site for 4 hours after vaccination. Safety procedures:

All subjects providing informed consent will undergo review of medical history, a general physical examination including vital signs measurement (temperature, respiratory rate, heart rate, blood systolic and diastolic pressure) at the screening visit (study Days 21 to-1)

and at Visit 1 (Day 1). At clinic Visit 2 and at subsequent visits, a brief symptom-directed physical examination (if necessary according to symptoms the subject has reported) will be performed.

For all women of childbearing potential before vaccination at visit 1, a urine pregnancy test will be conducted and will also be repeated at visit 5 (Day 85).

Procedure for Collection of Solicited AEs:

Beginning in the evening following study vaccine administration (approximately 6 hours), and daily during the 6 days following vaccination, diary cards will be used to collect solicited local and systemic adverse events including other reactions (i.e. body temperature measurements and use of analgesics/antipyretics).

A reminder phone call will be performed or an email will be sent by the site staff to the subject 2 and 6 days following vaccination to remind subjects that the diary card should be completed. Seven days following vaccination, a clinical visit (Visit 2) will be performed at the study site and all information recorded in the diary card will be reported on e-CRF.

In addition to the solicited adverse events data, any unsolicited AE, solicited local and systemic AE that continue at 7 days after study vaccination (Visit 2), will be collected and recorded at V2, V3 and V4 by clinical study staff.

All Serious Adverse Events (SAEs), all AEs leading to vaccine/study withdrawal, all Adverse Events of Special Interest (AESI, see below) and all concomitant medications associated with those events, will be collected from the time of vaccination (visit 1) to study termination (visit 5).

Reactive arthritis and neutropenia will be collected and analyzed as AESIs for this study.

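### The adverse event classes to be collected between Visit 4 and Visit 5 differ from section to section, yet the SAP reports unsolicited events in a single interval to study termination

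*Protocol*

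**What the plan says.** Protocol Version 2, section 7.1, sets the general window: "For the purpose of this trial, AEs will be from the time the subject signs informed consent until Visit 4". For the period up to Visit 5 it then names four classes: "serious, clinically significant as judged by the investigators, medically attended and AESI will be collected until study termination at visit 5".

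Other places give other lists for the same period:

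- Protocol 5.5 (Visit 5): "interview of subject to collect: medically attended adverse events, AEs leading to withdrawal, SAEs, AESIs, and new onset of chronic disease". Table 2 marks the same classes at Visit 5, and its row for all AEs has no Visit 5 mark.
- The protocol synopsis and SAP section 2 stop unsolicited AEs at Visit 4. From vaccination to Visit 5 they list "All Serious Adverse Events (SAEs), all AEs leading to vaccine/study withdrawal, all Adverse Events of Special Interest (AESI, see below") and nothing more.
- Protocol 3.1 is close to the synopsis, but among neutropenias it names only severe ones.
- Protocol 5.5.1 (early termination): "interview of subject to collect unsolicited adverse events, medically attended adverse events, AEs leading to withdrawal, SAEs, AESIs, and new onset of chronic disease". It states no Visit 4 limit.

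For laboratory results, 7.1.7 adds a rule with no visit limit: "Any abnormality in laboratory measurements classified as clinically significant must be reported in the Adverse Event CRF form".

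On the analysis side, Protocol 8.4.2.1.3 plans AE summaries by observation interval, with separate summaries for new-onset chronic disease and for medically attended events. SAP 6.5.2.3 uses one interval, Day 1 to study termination. Secondary safety endpoint (c) (Protocol 8.1.2.1, SAP section 4) counts subjects with unsolicited AEs of every type and grade over 84 days.

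**The concern.** Site staff cannot follow all of these lists at once. Whether a given event after Visit 4 reaches the AE form depends on which section was used to build the Visit 5 checklist or the case report form.

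The SAP table then shows one count per group over the whole study. A reader will take it as the number of subjects with any unsolicited AE in 84 days. In fact it is full collection for about four weeks plus selective collection for about eight, and the uniformly collected part is never shown alone. The number of days on which a subject was asked about all unsolicited events may also depend on whether the subject left early.

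**Working it through.** The plan gives no figure to reproduce here, so the check is a side-by-side reading followed by simple arithmetic.

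**Classes named for Visit 4 to Visit 5**

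| Class | 7.1 | 5.5 and Table 2 | 3.1 | Synopsis and SAP 2 | 5.5.1 |
|---|---|---|---|---|---|
| Serious | yes | yes | yes | yes | yes |
| AESI | yes | yes | reactive arthritis, severe neutropenia | yes | yes |
| Leading to withdrawal | no | yes | yes | yes | yes |
| Medically attended | yes | yes | no | no | yes |
| New-onset chronic disease | no | yes | no | no | yes |
| Judged clinically significant | yes | no | no | no | only as an unsolicited AE |
| Any other unsolicited AE | no | no | no | no | yes |

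Only serious events are treated identically everywhere.

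**Test case 1.** Take a non-laboratory AE on Day 60 that the investigator judges clinically significant, but that is not serious, medically attended, an AESI, a new chronic disease or a reason for withdrawal. Section 7.1 collects it. It is absent from 5.5, Table 2, 3.1, the synopsis and SAP section 2.

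**Test case 2.** Take a medically attended AE, or a new chronic disease, first reported at Visit 5. Section 5.5 and Table 2 collect both. The synopsis and SAP section 2 name neither, although Protocol 8.4.2.1.3 promises a summary of each.

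**Test case 3.** Take a minor unsolicited AE on Day 50. A completer is not asked about that class at Visit 5. A subject who leaves on Day 60 and is seen under 5.5.1 may be.

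**Test case 4.** Take a clinically significant blood count at Day 85. Section 7.1 defines AEs to include it ("an AE can be any unfavorable and unintended sign (including an abnormal laboratory finding, for example"), 7.1.7 sends it to the AE form, and SAP 6.5.2.3 counts it once recorded. The shorter lists merely do not mention it.

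**Length of the restricted period**

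- Nominal: 84 − 28 = 56 days; 56/84 = 66.7%.
- With the Table 2 windows (Visit 4: −3 to +4; Visit 5: −3 to +7), shortest: (84 − 3) − (28 + 4) = 49 days.
- Longest: (84 + 7) − (28 − 3) = 66 days.

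**Weight of one event**

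- Planned primed subjects (Table 1): 5 + 4 + 2 + 4 + 5 = 20, so one subject is 1/20 = 5.0 percentage points.
- Planned placebo plus naïve subjects: 4 + 26 = 30, so one subject is 1/30 = 3.3 points.

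The documents give neither an expected rate of such events nor an expected number of subjects leaving between Visits 4 and 5, so no total effect can be calculated.

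**The case against.** The best reply is that the lists serve different purposes. Section 5.5 describes what is asked at interview, and laboratory results do not come from an interview. Table 2 marks haematology at Visit 5 and points to 7.1.7. Section 3.1 and the synopsis are summaries, and 3.1 refers to sections 5 and 7 for detail. SAP section 2 describes the design; the counting rule is 6.5.2.3. The early termination list must include unsolicited AEs because it also serves exits before Visit 4 and subjects never vaccinated.

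Much of this stands. In particular, a reader might infer that a clinically significant Day-85 blood count is an AE under some sections and not under others. The documents do not support that. No section says it is not an AE, 7.1 and 7.1.7 agree, and SAP 6.5.2.5 lists all laboratory results for subjects with a clinically significant value in any case. The 5.5.1 wording also does not expressly override the Visit 4 limit, so different questioning of early leavers is possible rather than certain.

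The reply does not remove the rest. A non-laboratory AE judged clinically significant would come to light at interview, and the interview list omits it. Referring 3.1 to sections 5 and 7 does not help, because those sections themselves differ. Nothing states that the lists are to be combined.

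**Conclusion.** The point holds as an inconsistency in AE collection after Visit 4, with a direct consequence for one table: the SAP's single-interval count of unsolicited AEs mixes complete with partial collection over about 56 of 84 days (49 to 66 with visit windows). Each event affected moves a group rate by 5.0 or 3.3 points at the planned sizes, and by more if fewer subjects enrol.

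A reader might go further and infer a biased comparison between the primed and first-dose groups. The documents do not show that. All subjects attend one open-label centre under the same instructions, no mechanism acting differently by group is evident, the number of early leavers is unknown, and SAP section 7 makes all analyses descriptive. The primary immunogenicity objective and the laboratory tables are not affected.

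A related loose end belongs to the same reconciliation: 3.1 limits the neutropenia AESI to severe cases, and 7.1.4.1 ties its definition to 7 days after vaccination, so the status of a Day-85 neutropenia as an AESI is unclear. Those passages must be reconciled.

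**What to change.** 1. Write one list for Visit 4 to Visit 5 from the classes the protocol already names, and use it in 7.1, the synopsis, 3.1, Table 2, 5.5, 5.5.1 and SAP section 2. Which classes to keep is the sponsor's choice. If a class is dropped, the summaries promised for it in 8.4.2.1.3 need changing too.
2. In the shorter lists, add a cross-reference to 7.1.7 for clinically significant laboratory results.
3. In SAP 6.5.2.3, report all unsolicited AEs with onset up to Visit 4, applying the same cut to early terminators, and report the restricted classes to Visit 5 separately.
4. Reword endpoint (c) in the synopsis, Protocol 8.1.2.1 and SAP section 4 to match. Otherwise the new SAP table would contradict its own endpoint.

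The cost is a wording amendment and one onset filter in the programming. No visit or blood draw is added.
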